**INTERMITTENT VERSUS CONTINUOUS SUCTION TECHNIQUE IN THE DIAGNOSIS OF
PANCREATIC SOLID LESIONS. A PILOT STUDY**

STUDY PROTOCOL 03/02/2019

NCT03829748

PRINCIPAL INVESTIGATOR

Dra. [name]

SUB-INVESTIGATORS

[name] [name]

[name] [name]

Gastroenterology Department, Endoscopy Unit

Hospital Universitario de la Princesa

Madrid, Spain

1. INTRODUCTION:

Solid lesions of the pancreas can be neoplastic or non neoplastic and it is important to accurately differentiate between them because of the poor prognosis related to pancreatic neoplasm. There are many types of solid pancreatic lesions: pancreatic adenocarcinoma, neuroendocrine tumor, lymphoma, solid pseudopapillary neoplasm and pancreatic metastasis.

There are several diagnostic methods for the study of pancreatic solid lesions. The different imaging test allow detection and characterization of those lesions, but most times an anatomopathological diagnosis is needed before establishing the most appropriate treatment.

Endoscopic Ultrasound guided fine needle aspiration (EUS-FNA) is the diagnostic method of choice for the diagnosis of these lesions as it detects small lesions that sometimes cannot be found in radiological imaging test, evaluates vascular invasion and the presence of liver metastasis, and allows pancreatic puncture for a cytological diagnosis. EUS-FNA is the safest technique for pancreatic puncture and the least related to needle track seeding.

In order to gather as much material as possible different techniques have been proposed:

- Fanning technique and multiple pass technique: to guide the needle into different regions of the target lesions with or without removing the needle out of the lesion depending on whether the lesion is hard or soft.
- Use of stylet: there are no data clearly demonstrating that the use of suction increases the yield of EUS-FNA. Some authors do slow withdrawal of the stylet.
- Size of the needle: 19 gauge, 22 gauge, 25 gauge, depending on the localization, size and vascularization. There is increasing evidence that smaller needles offer at least similar results in diagnostic yield compared to larger needles and are also easier to manipulate.
- Use of suction: there is conflicting evidence in this point. Several studies have evaluated the use of high volume aspiration vs low volume aspiration, continuous aspiration vs no aspiration and suction with empty syringe vs water-filled syringe but none is clearly better than other.

2. HIPOTESIS:

Intermittent suction improves the diagnostic yield of pancreatic lesions compared to standard (continuous) suction. Up to our knowledge this method has not been yet evaluated.

3. STUDY DESIGN:

Interventional study with diagnostic purpose, longitudinal, prospective, unicentric, blinded for participant and anatomopathologist, in patients with solid pancreatic lesions with indication of cytological sampling by Endoscopic Ultrasound referred to the Endoscopy Unit of Hospital Universitario de la Princesa from January 2019 to December 2019.

Following clinical practice, an endoscopic ultrasound fine-needle aspiration (EUS-FNA) with a 25 gauge needle will be performed to each participant. The patients will be divided into two arms with a 1:1 ratio:

- a) Intermittent aspiration: Intervention arm. Endoscopic ultrasound will be done for the localization of the lesion and to localize the site of puncture. Prior to the puncture of the lesion the stylet is removed and a vacuum syringe is prepared with 10 cc of vacuum allowing the generation of continuous pressure inside and connected to the end of the needle. Once the lesion is punctured 15 movements in and out of the lesions will be made while the syringe is opened and closed on and off for a total of 3 times each pass. A total of 4 passes will be done in each lesion.
- b) Continuous/standard aspiration: Same procedure but once the lesion is punctured 15 movements in and out of the lesions will be made while the syringe remains opened.

Randomization will be done with the generation of a computer-generated random list using Epidat 4.0. software (SERGAS®, Santiago de Compostela, Spain).

The endoscopic ultrasound will be done with an Olympus linear echoendoscope (GF-UTC 260 Olympus® Tokyo, Japan) under Propofol sedation by an Anesthesiologist.

Each pass will be sent to the pathologist separately to evaluate their individual characteristics and to determine which one is diagnostic. A complete report will be done assessing:

- a) Cellularity
- b) Hematic contamination
- c) Presence of cell block and possibility of doing immunohistochemistry

4. OUTCOME MEASURES:

- a. Primary outcome measure: Increase in diagnostic yield of pancreatic solid lesions
- b. Secondary outcomes:
 - Sample Celularity: Number of malignant cluster of cells on each endoscopic pass
 - Blood contamination: Percentage of blood contamination of the slides
 - Number of passes to reach a positive cytological diagnosis

5. ELEGIBILITY CRITERIA:

- a) Inclusion Criteria:
 - Pancreatic solid lesion
 - Patients over 18 years old
 - Suitable for endoscopy
- b) Exclusion Criteria:
 - Contraindication for endoscopy
 - Active anticoagulant therapy
 - Thrombocytopenia or coagulopathy in the absence of its correction prior to the procedure
 - Absence of informed consent
 - Pregnancy
 - Not accessible lesion for endoscopic ultrasound puncture

6. STATISTICAL ANALYSIS PLAN:

Data will be expressed as means and standard deviation for quantitative variables or frequencies and percentages for the categorical ones. Variables with non-normal distributions will be represented as means and percentage ranges.

Randomization will be done with a computer-generated random list in a 1: 1 ratio. The chi-square test will be used to compare qualitative variables. Correlation kappa values will be offered between both methods. In order to evaluate the differences in diagnostic yield, the sensitivity after the completion of each pass will be calculated by correlating the continuous values of confusion with the final cytology with the Spearman test. The number of optimal passes depending on the method will be calculated by maximizing that the following passes would not modify the additional diagnostic yield more than 10% over the accumulated one. On the other hand, the cellularity and blood contamination graduated in its three levels will be contrasted between both methods with an analysis of McNemar. All the variables that could potentially modify the diagnostic yield of both methods will be compared with univariate and later multivariate analysis by means of logistic regression analysis with the STATA application (v13.0, StataCorp, College Station, Texas, USA). The protocol will be approved by the Ethical Committee of the Hospital Universitario de la Princesa before the start of the study.

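### A pilot of unstated size asks whether intermittent suction improves yield, but no planned analysis gives the between-arm difference in yield with its precision

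*Combined protocol and SAP*

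**What the plan says.** The title ends "PANCREATIC SOLID LESIONS. A PILOT STUDY". Section 2 gives one hypothesis, and it is directional: "Intermittent suction improves the diagnostic yield of pancreatic lesions compared to standard (continuous) suction". It adds "Up to our knowledge this method has not been yet evaluated", so no earlier estimate of the effect is claimed.

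Section 3 sets the allocation ("The patients will be divided into two arms with a 1:1 ratio") and limits recruitment by calendar and centre only: patients "referred to the Endoscopy Unit of Hospital Universitario de la Princesa from January 2019 to December 2019". Section 4 gives the "Primary outcome measure: Increase in diagnostic yield of pancreatic solid lesions", with no size of increase and no statement of the pass after which yield is judged.

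Section 6 says "The chi-square test will be used to compare qualitative variables". For yield in particular it says "In order to evaluate the differences in diagnostic yield, the sensitivity after the completion of each pass will be calculated", and it then names a Spearman correlation with the final cytology. It also lists kappa, McNemar for cellularity and blood contamination, a rule for the optimal number of passes, and univariate then multivariable logistic regression.

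No section gives a target number of patients, an assumed control yield, an effect of interest, an alpha, a precision aim, or a confidence interval for the difference in yield between arms. No section says how a non-significant comparison would be interpreted.

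**The concern.** A small first study of an untested technique can usefully report how far apart the two yields are and how uncertain that gap is. As section 6 stands, neither quantity is planned. Chi-square gives a test statistic. A Spearman coefficient between by-pass results and final cytology measures association with a reference; it is not a contrast between arms.

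Readers would therefore have to judge a superiority hypothesis from tests whose sensitivity nobody has set. If the study turns out small, two things follow:

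- A non-significant test may be taken as evidence against the technique although a worthwhile gain remains compatible with the data.
- A significant test will tend to come with an inflated estimate, which is a poor basis for adopting the technique or sizing a later trial.

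**Working it through.** **Inputs.** From the documents: 1:1 allocation, independent arms, and chi-square for categorical comparisons. The plan states no sample size or power, so it has no figure to reproduce. Assumed: per-patient yield (diagnostic or not), uncorrected chi-square, two-sided alpha 0.05, no dropout, continuous-suction yield of 70% to 85%, and 20 to 200 patients per arm.

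**Power and exaggeration.** With x1 and x2 diagnostic results among n per arm, d = (x2 - x1)/n and p = (x1 + x2)/(2n). The statistic is X² = d² / [2p(1 - p)/n], significant if it exceeds 3.84. Power is the sum of the two binomial probabilities over all significant pairs (x1, x2). The exaggeration ratio is the mean of |d| among significant results divided by the true difference.

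| True yields | n per arm | Power | Mean significant difference (points) | Ratio to truth |
|---|---|---|---|---|
| 80% v 90% | 20 | 14% | 27 | 2.7 |
| 80% v 90% | 30 | 19% | 22 | 2.2 |
| 80% v 90% | 50 | 30% | 18 | 1.8 |
| 80% v 90% | 100 | 52% | 14 | 1.4 |
| 80% v 90% | 200 | 81% | 11 | 1.1 |
| 70% v 90% | 30 | 50% | 28 | 1.4 |
| 85% v 90% | 30 | 10% | 20 | 3.9 |

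With a real 80% v 90% difference, the chance of a non-significant result is 100 - 19 = 81% at 30 per arm and 100 - 30 = 70% at 50 per arm.

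**Why the ratio exceeds 1.** Suppose 24 of 30 are diagnostic with continuous suction. Then 28 of 30 with intermittent suction gives X² = 2.31 (not significant) and 29 of 30 gives X² = 4.04 (significant). In that case no gain below 5/30 = 16.7 points reaches significance, so a true 10-point gain can be significant only when overestimated.

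**What a non-significant result leaves open.** Take 24/30 (80%) v 27/30 (90%): X² = 1.18, p = 0.28. The Wilson 95% limits are 0.627 to 0.905 and 0.744 to 0.965. The Newcombe limits for the difference are:

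- lower: 0.10 - √[(0.900 - 0.744)² + (0.905 - 0.800)²] = 0.10 - 0.188 = -0.088
- upper: 0.10 + √[(0.965 - 0.900)² + (0.800 - 0.627)²] = 0.10 + 0.185 = +0.285

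The interval, about -9 to +29 points, contains both no gain and a gain far larger than the one assumed.

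**The case against.** **The size of the exaggeration is not in the documents.** A reader might infer that any significant result will overstate the benefit about twofold. The plan does not support that. With sample size, control yield and true gain all unstated, the ratio at 30 per arm alone runs from 1.4 to 3.9, and for 80% v 90% it falls to 1.1 at 200 per arm. Twofold is one point in a range. This objection stands in full, and the figures here are conditional for that reason.

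**The plan contains no decision rule.** A reader might also infer that the study is bound to conclude either that the technique improves yield or that it does not, and that a null result will be reported as no difference. Section 6 gives no alpha, no p-value threshold and no rule for null results, and a directional hypothesis is not a decision rule. What stands is narrower: the plan does not say how its tests will be interpreted.

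**Chi-square may not be the test of yield.** Section 6 assigns chi-square to qualitative variables in general and Spearman to yield. Applying chi-square to per-patient yield is a natural reading, but it is an inference, and the power figures depend on it. The gap does not, because the Spearman route gives no between-arm difference either.

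**Section 6 does plan some estimates.** Percentages, kappa, sensitivity by pass and logistic regression are listed. That is fair, but none is specified as the yield difference between arms with an interval. The regression is described for variables that might modify yield, without naming the arm effect as its result.

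**The study might recruit well.** The documents give no referral volume, so a large sample cannot be excluded, and nothing here supports advice for or against enlarging the study.

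**Conclusion.** The concern holds in limited form. A study labelled a pilot, with no stated size, has a superiority hypothesis as its only aim, and its named analyses provide neither the between-arm difference in yield nor its precision. That much is read directly from the title and sections 2, 3, 4 and 6.

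The numerical consequence depends on assumed yields, sample sizes, two-sided 0.05 and a per-patient chi-square test. At 20 to 50 per arm with a true 10-point gain from 80%, power is 14% to 30% and significant results are inflated 2.7 to 1.8 times on average. The inflation is smaller for larger effects or samples and greater for smaller effects. At 30 per arm a non-significant 10-point gain would leave a useful benefit open. This is a matter of what the analysis reports and how it is interpreted. It should be corrected, but it does not invalidate the design.

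**What to change.** Change the wording of sections 2, 4 and 6:

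- **Section 2:** restate the aim as estimating the difference in diagnostic yield between intermittent and continuous suction.
- **Section 4:** define the primary result as the per-patient difference in diagnostic yield, intermittent minus continuous.
- **Section 6:** report that difference with a Newcombe 95% CI, in place of the Spearman analysis of yield. State that the conclusion rests on the estimate and its interval, and that a non-significant test will not be taken as no difference. If chi-square is kept for yield, label it supportive, because the two can disagree at the margin: 24/30 v 29/30 gives p = 0.044 but a Newcombe interval of about -0.3 to +34.2 points.

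A criterion for proceeding to a larger trial would be a reasonable addition but is optional.

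The cost is text only, with no extra patients, procedures or data. The downside is that the pilot gives up a confirmatory claim based on a p-value.

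### The primary outcome is diagnostic yield in solid pancreatic lesions of any kind, but section 6 evaluates it as sensitivity for an unstated target condition, so reference-negative lesions leave the comparison

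*Combined protocol and SAP*

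**What the plan says.** The hypothesis in section 2 is that "Intermittent suction improves the diagnostic yield of pancreatic lesions compared to standard (continuous) suction". Section 4 carries this into the outcome list: "Primary outcome measure: Increase in diagnostic yield of pancreatic solid lesions". Neither section gives a numerator, a denominator or a time point for yield.

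The population is broad. Section 3 describes recruitment "in patients with solid pancreatic lesions with indication of cytological sampling by Endoscopic Ultrasound", and the only inclusion criterion in section 5 about the lesion is "Pancreatic solid lesion". No exclusion is based on pathology. The introduction states that "Solid lesions of the pancreas can be neoplastic or non neoplastic and it is important to accurately differentiate between them".

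Section 6 then says: "In order to evaluate the differences in diagnostic yield, the sensitivity after the completion of each pass will be calculated". It continues that this will be done "by correlating the continuous values of confusion with the final cytology with the Spearman test". It does not say whether a positive result means malignancy, neoplasia or any specific diagnosis. Malignancy appears in section 4 only in the cellularity outcome, and the positive cytological diagnosis in the number-of-passes outcome is not defined.

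Section 3 also says that each of the four passes goes separately to the pathologist, who judges which passes were diagnostic.

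**The concern.** Yield and sensitivity have different denominators. Yield, in its ordinary sense, is taken over every lesion sampled and asks whether the sample gave a diagnosis. Sensitivity is taken only over lesions positive on the reference and asks how many of them the sample detected. A lesion negative on the reference counts as neither a success nor a failure for sensitivity, whatever the quality of its sample.

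Two things are at stake. First, the hypothesis concerns lesions in general, so an effect of suction technique on sampling in reference-negative lesions belongs to the question but does not enter the measure. Second, reference status is known only after randomisation and sampling. If the reference is itself built from the study passes, the suction technique can influence which lesions are in the denominator. The comparison is then no longer between the groups as randomised.

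**Working it through.** The plan states no expected yield, sensitivity, case mix or sample size, so it has no figure to reproduce. The check has three steps.

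**Step 1. Who leaves the denominator under each possible target condition**

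| Target condition | Lesions left out of sensitivity |
|---|---|
| Malignancy | Non-malignant lesions |
| Neoplasia | Non-neoplastic lesions |
| Any specific diagnosis on final cytology | Lesions never diagnosed |

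Sensitivity keeps all enrolled lesions only if none is reference-negative, and nothing in sections 3 or 5 ensures that.

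**Step 2. Size under the first two readings (assumed values)**

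Let m be the share of reference-positive lesions (the same in both arms), Se the sensitivity, and Yn the share of reference-negative lesions with a diagnostic sample. A missed reference-positive lesion counts as a yield failure. Then

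yield over all lesions = m × Se + (1 − m) × Yn

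difference in yield = m × (difference in Se) + (1 − m) × (difference in Yn).

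Assume Se is 85% v 90%, a difference of 5 points. Case A has Yn 60% v 80%, a gain of 20 points. Case B has no gain in Yn.

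| Reference-negative | Case A | Case B | Sensitivity shows |
|---|---|---|---|
| 10% | 0.9 × 5 + 0.1 × 20 = 6.5 | 0.9 × 5 = 4.5 | 5 |
| 20% | 0.8 × 5 + 0.2 × 20 = 8.0 | 0.8 × 5 = 4.0 | 5 |
| 30% | 0.7 × 5 + 0.3 × 20 = 9.5 | 0.7 × 5 = 3.5 | 5 |

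Sensitivity understates the yield difference in case A and overstates it in case B.

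A second assumed set uses Se 80% v 90%, a difference of 10 points, and m from 70% to 90%. The widest results are at m = 70%. If Yn is 50% v 70%, the yield difference is 0.7 × 10 + 0.3 × 20 = 13 points. If Yn is 70% v 50%, it is 0.7 × 10 − 0.3 × 20 = 1 point.

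**Step 3. The third reading**

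If the target is any specific diagnosis, the lesions left out are those that were never diagnosed, which are the yield failures themselves. Suppose also that the final cytology is the combined result of the same four passes, and that each pass is independently diagnostic with probability p. Then

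yield after k passes = 1 − (1 − p)^k

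sensitivity after k passes = [1 − (1 − p)^k] / [1 − (1 − p)^4].

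At k = 4 the sensitivity is 100% for any p. The yield after four passes is 76% for p = 0.3, 94% for p = 0.5 and 99% for p = 0.7. If one arm had p = 0.3 and the other p = 0.5, the yields would differ by 93.75 − 75.99 = 17.8 points, while sensitivity after the fourth pass would be 100% in both arms.

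**The case against.** The strongest reply is that section 6 does not commit the trial to sensitivity alone. It also names a chi-square test for qualitative variables, a 10% rule on accumulated yield, and logistic regression for variables that could modify yield. None is restricted by lesion type, and any of them could be applied to yield over all lesions. This stands in part: section 6 designates no single primary analysis, so it cannot be said that the reported primary result will be a sensitivity. But the chi-square sentence is generic, the regression concerns modifiers, and the 10% rule chooses a number of passes. Only the sensitivity sentence is offered as the way to evaluate differences in yield.

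It is also fair to say that suction effects in reference-negative lesions are not wholly lost. Blood contamination is a secondary outcome with no restriction by lesion type. That does not repair the primary outcome.

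A reader might go further than the documents allow in three ways:

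- **That every non-malignant lesion is excluded.** This needs malignancy to be the target condition. The cellularity outcome hints at it, but section 6 does not state it, and the introduction contrasts neoplastic with non-neoplastic lesions. Which lesions drop out depends on a choice the plan has not made.
- **That sensitivity understates the benefit.** Case B shows the opposite, and the documents give no basis for preferring case A.
- **That losing these lesions inflates the standard error by 1/√m.** This would hold only if the variance were the same for both measures. In case A the yields are 82.5% v 89%, 80% v 88% and 77.5% v 87%. For equal arms, the ratio of standard errors is √{[0.85 × 0.15 + 0.90 × 0.10]/m} divided by √{sum of y(1 − y) over the two arms, with y the yield}. This gives 0.999, 1.012 and 1.040, so no loss of precision worth claiming follows.

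**Conclusion.** The concern holds in this form: yield is undefined, and the one sentence that says how to evaluate it replaces it with sensitivity for an unstated target condition. Lesions negative on the reference then leave the comparison. On any of the three readings, the measure differs from yield over all lesions as soon as some enrolled lesions are reference-negative. The two differences between arms coincide only if there are no such lesions, or if those lesions show the same gain between arms as the others.

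The size cannot be fixed from the documents. Under the assumed values, a 5-point sensitivity difference goes with a yield difference of 3.5 to 9.5 points, and a 10-point one with 1 to 13 points. The direction is open. These ranges rest on assumed case mix and assumed performance in reference-negative lesions, and they apply to the malignancy and neoplasia readings. The loss of all contrast after the fourth pass applies only if the target is any specific diagnosis and the final cytology comes from the same four passes.

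This should be corrected, because it determines which question the primary comparison answers.

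**What to change.** In sections 4 and 6, define the primary outcome as the proportion of all randomised patients with at least one pass judged diagnostic (malignant or specific benign) by the blinded pathologist after the fourth pass. Fix the handling of equivocal samples in advance, since the documents do not mention them. Name the comparison of this proportion between arms, by the chi-square test already in section 6, as the single primary analysis. Keep sensitivity after each pass as a secondary outcome, with its target condition and reference standard stated.

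The cost is a few sentences. No new data are needed, because every pass is already assessed separately and judged diagnostic or not. The downside is that the headline figure may be somewhat lower than a sensitivity, since insufficient samples from all lesions count as failures.

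### Cellularity and blood contamination: McNemar has no pairs to work on in this parallel design, the unit of analysis is unstated, and pooling the four passes would inflate the false-positive rate

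*Combined protocol and SAP*

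**What the plan says.** - **Allocation (Section 3).** "The patients will be divided into two arms with a 1:1 ratio". Each patient is sampled with one suction method only.
- **Passes (Section 3).** For the intermittent arm, "A total of 4 passes will be done in each lesion". The continuous arm is described by reference to it ("Same procedure but once the lesion is punctured 15 movements in and out of the lesions will be made while the syringe remains opened"), so it also has four.
- **Reporting (Section 3).** "Each pass will be sent to the pathologist separately to evaluate their individual characteristics and to determine which one is diagnostic". The report covers cellularity and hematic contamination.
- **Outcomes (Section 4).** Cellularity is "Number of malignant cluster of cells on each endoscopic pass". Blood contamination is "Percentage of blood contamination of the slides", with no mention of the pass in that line.
- **Analysis (Section 6).** "the cellularity and blood contamination graduated in its three levels will be contrasted between both methods with an analysis of McNemar". A general sentence adds: "The chi-square test will be used to compare qualitative variables".

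Section 6 names no patient random effect, GEE, robust variance or per-patient summary for these endpoints. The document states no significance level, sample size or ICC.

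**The concern.** There are two linked problems.

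1. **The test does not fit the data.** McNemar compares two binary readings on the same or matched units. Here the two methods are used in different patients, so nothing links a reading in one arm to a reading in the other, and the grade has three levels. Bowker's extension copes with three levels but still needs pairs. Any pairing would have to be invented, and the p-value would depend on how it was done.

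2. **Passes from one lesion are not independent.** Section 1 says that lesions differ in hardness and vascularization, and the passes into one lesion share these features. For cellularity there is a further reason. The count is of malignant clusters, eligibility requires only a solid pancreatic lesion (Section 5), and Section 1 says that such lesions may be non-neoplastic. A non-malignant lesion should score about zero on all four passes, whereas a malignant one can score above zero on each.

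An analyst who saw the first problem might repair it with a chi-square test on all passes. That would leave the second in place: standard errors too small, and a difference between suction methods declared too readily.

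**Working it through.** The plan gives no error rate, power or sample size for these endpoints, so there is no figure of its own to reproduce.

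**Inputs**
- From the documents: passes per patient m = 4 (Section 3), a three-level grade (Section 6), parallel arms in a 1:1 ratio (Section 3).
- Assumed: two-sided alpha 0.05; 20, 30 or 50 patients per arm; between-pass ICC from 0 to 0.7; three equally likely grades.

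**Step 1: formula.** If passes are pooled as independent, the variance is understated by the design effect DE = 1 + (m - 1) × ICC = 1 + 3 × ICC. The actual two-sided error is 2 × [1 - Φ(1.96/√DE)]. Here the ICC is that of the quantity actually tested.

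| ICC | DE | Actual error |
|---|---|---|
| 0 | 1.00 | 5.0% |
| 0.05 | 1.15 | 6.8% |
| 0.1 | 1.30 | 8.6% |
| 0.2 | 1.60 | 12.1% |
| 0.3 | 1.90 | 15.5% |
| 0.5 | 2.50 | 21.5% |
| 0.7 | 3.10 | 26.6% |

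**Step 2: null simulation.** A latent normal value per pass, with a shared patient component, was cut into three grades (10,000 trials per setting). Cutting weakens the correlation, so the latent and observed ICC differ. Results for 30 per arm, all four passes pooled:

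| Latent ICC | Observed-grade ICC | Chi-square, 3 levels | McNemar, top grade vs rest, arbitrary pairs | Bowker, arbitrary pairs |
|---|---|---|---|---|
| 0 | 0.00 | 4.9% | 4.7% | 4.5% |
| 0.1 | 0.08 | 7.2% | 7.1% | 6.4% |
| 0.3 | 0.24 | 11.7% | 11.4% | 10.1% |
| 0.5 | 0.41 | 17.6% | 16.6% | 15.6% |
| 0.7 | 0.59 | 24.4% | 20.9% | 22.9% |

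Results at 20 and 50 per arm are similar. Further runs give about 6% at latent ICC 0.05 and about 8-10% at 0.2 for the pooled chi-square and McNemar. These rates are lower than in Step 1 at the same nominal ICC, mainly because the observed-grade ICC is lower than the latent one.

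**Step 3: interval width.** The ratio of naive to correct width is 1/√DE, using the observed-grade ICC.
- Latent 0.2, observed 0.16: DE = 1 + 3 × 0.16 = 1.48; ratio = 1/√1.48 = 0.82.
- Latent 0.7, observed 0.59: DE = 1 + 3 × 0.59 = 2.77; ratio = 1/√2.77 = 0.60.

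**Step 4: one value per patient.** Over all settings, a chi-square on a single pass rejects in 4.7-5.4% of null trials and a t-test on patient means in 4.5-5.5%. A Wilcoxon test on patient means also stays near 5% (4.0-5.8% in runs of 2,000). Bowker on one pass with arbitrary pairs gives 2.6-4.6%: not inflated, but still resting on invented pairs. The mixed model and GEE were not simulated.

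**The case against.** A reader might infer that the planned analysis will produce false-positive rates well above 5%. The documents do not support that. It needs all four passes to be entered as independent rows, and it needs a material ICC. Section 6 states neither. It names no unit, the blood contamination line in Section 4 refers to slides rather than passes, and the diagnostic-yield analysis in Section 6 proceeds pass by pass. Comparing the arms at a given pass, or on one grade per patient, is therefore also a possible reading, and Step 4 shows no inflation under it. At low correlation even pooling does little harm: about 6% in simulation, or 6.8% by formula, at ICC 0.05. This objection stands, and the rates here are conditional for that reason.

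It is also fair to say that Section 6 assigns McNemar, not chi-square, to these endpoints, so a chi-square error rate alone would describe a different analysis. The arbitrarily paired McNemar and Bowker results meet this: they are inflated to a similar degree.

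Finally, the plan promises no confidence intervals for these endpoints, so the width ratios matter only if intervals are reported.

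The objection does not rescue the plan as written. No choice of unit gives McNemar its pairs. Because cellularity is defined per pass and no summary is specified, pooling is a natural reading. An ICC near zero is implausible for a count of malignant clusters; the argument is less direct for blood contamination.

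**Conclusion.** The point holds in conditional form. What follows from the documents alone is that McNemar does not suit unpaired three-level data, that the unit of analysis is not stated, and that no provision is made for four correlated passes per patient.

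The size depends on assumptions. If passes are pooled, the false-positive rate at an assumed nominal 5% would be about 6-7% at latent ICC 0.05-0.1, 8-12% at 0.2-0.3, 16-18% at 0.5 and 21-25% at 0.7, for pass-level chi-square or arbitrarily paired McNemar with 20-50 patients per arm. Pooled intervals would be about 0.82 to 0.60 of the correct width at latent ICC 0.2-0.7.

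The consequence is limited. These are secondary endpoints in a study titled a pilot, and a reader should not carry this point over to diagnostic yield, the primary outcome. It should be corrected because the comparison is invalid as written and the remedy is cheap.

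**What to change.** In Section 6, replace McNemar for these two endpoints with an unpaired comparison and state that the patient is the unit of inference. Prespecify one of:

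- **Per-patient summary:** the mean grade over the passes, compared between arms with a two-sample Wilcoxon test.
- **Pass-level model:** an ordinal mixed model with a patient random effect, or an ordinal GEE with the patient as the cluster, with arm and pass number as covariates.

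State also that blood contamination is analysed from the per-pass reports, and handle it in the same way. Do not substitute a chi-square test on passes: it removes the pairing fault but keeps the clustering fault.

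The cost is SAP wording and, for the model, slightly more complex code. Intervals will be wider than those from a naive pooled analysis. No change to data collection is needed, since each pass is already reported separately.
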